In the implementation of EIT-4-BPSD we will build on our prior work and that of others. We will train staff to reduce BPSD, address unmet resident needs, optimize function and physical activity, promote quality of life and reduce adverse events. Specifically, we will work with facilities to establish appropriate environments and

policies, use individualized approaches based on resident preferences, use person-centered communication skills and optimize function during care interactions. Further we will emphasize teamwork, ongoing quality improvement, and use of motivational techniques to engage residents in appropriate activities.

B. Innovation

The proposed study offers the following innovations:

1. To our knowledge, there have been no systematic attempts to facilitate implementation of best practices for BPSD in nursing homes using EIT. Our approach addresses several gaps identified in a recent systematic review of 54 implementation studies on behavioral approaches for dementia care.⁹⁴ Specifically, we use: (a) all 5 RE-AIM criteria for evaluation; (b) a flexible approach for implementation; (c) theoretically based behavior change techniques; (d) direct observation of staff behavior change; (e) monitoring of outcomes to 12 months post initial implementation of EIT-4-BPSD; and (f) we examine maintenance in EIT-4-BPSD facilities at 24 months post implementation (which is 12 month post intervention activities).
2. One size does not fit all with regard to successful implementation of interventions.³⁰ Use of the EIT allows for ongoing interaction through the use of a participatory implementation process in treatment facilities. Allowing facilities to identify their own facilitators and barriers to non-pharmacologic management of BPSD and take ownership of the solution will help assure successful implementation of EIT-4-BPSD.
3. Repeatedly it has been noted that staff tend to resume old behaviors 6 months following implementation of innovative interventions.^{95,96} We will address sustainability of EIT-4-BPSD by evaluating facility and resident outcomes at 12 months post initial implementation and maintenance at 12 months post completion of the intervention (24 months post implementation). We will use qualitative methods to understand challenges and facilitators associated with implementation of EIT-4-BPSD and evaluate the cost of implementation to guide future work.

C. Approach

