Real World Experience and Pilot Testing EIT-4-BPSD: Our team has expertise with regard to clinical work ([name], [name], [name]), administration ([name]) and regulations ([name]), and implementation of relevant innovative approaches to care (all investigators) in nursing homes. In addition, we have expertise in the education of minorities and nursing assistants([name], [name], [name], [name], [name]) and using qualitative methods ([name], [name], [name]) (see biosketches). We have pilot tested the EIT-4-BPSD in two facilities (one in Maryland and one in Pennsylvania) for feasibility and demonstrated that sites are willing to identify a Champion and Stakeholder team, engage in monthly face-to-face meetings (100% participation of stakeholders) and weekly email interactions (100% participation). We implemented all components of the intervention, recruited residents (recruitment rate of 50%) and completed measures without being burdensome to residents or staff. Building on our extensive preliminary work we will test EIT-4-BPSD in 50 nursing homes in Maryland and Pennsylvania.

Methods

Design: To achieve our Aims we will use a Hybrid III pragmatic cluster randomized clinical trial³² for two reasons: (a) implementation of EIT-4-BPSD requires a facility-wide approach; and (b) we need to prevent treatment contamination that might occur if we randomized within sites. Fifty nursing homes will be randomized to treatment (EIT-4-BPSD) or Education-Only Control (EO) using permuted-block randomization. Assignment will be concealed until after the facility consents to participate. Outcomes at the resident and facility level will be evaluated. Resident outcomes will be obtained at baseline, 4 and 12 months post implementation of the intervention. Facility outcomes will be obtained at baseline and 12 months post initial implementation. We will also examine Maintenance in EIT-4-BPSD facilities at 24 months post implementation.

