Once the nursing facility expresses an interest in participating in the study, the facility will be randomized to one of three cohort groups and then randomized to EIT-4-BPSD or EO. We will implement EIT-4-BPSD in 8-10 facilities and the EO intervention in 8-10 facilities during each cohort period. We recognize there will be a period of time between recruitment and implementation of study related activities and will keep facilities updated. In addition, we will maintain a waiting list of interested facilities in the event that some volunteer facilities decide not to participate (their data will be included in terms of Reach).

Resident Participants: We will keep our resident enrollment criteria to a minimum to increase external validity. Residents will be eligible to participate if they: (a) are living in a participating nursing home; (b) are 55 years of age or older; (c) have a history within the past month of exhibiting at least one BPSD; (d) have cognitive impairment as determined by a score of 0-12 on the Brief Interview of Mental Status (BIMS);¹²² (e) are not enrolled in Hospice; and (f) are not in the nursing facility for short-stay rehabilitation care. We will obtain a list of all eligible residents from a designated staff member and randomly approach each resident until 12-13 residents per facility are recruited by research assistants (RAs) (N= 625 residents). This sampling approach is used to assure variability and equal participation from each nursing facility in the study. Based on our prior research and recent data from the most recent Nursing Home Compendium¹²³ we conservatively anticipate that 25% to 30% of residents will be eligible.^{123,124} We are confident we will be able to recruit 12-13 residents per facility.^{8,77,125} See the Human Subjects section for details of the consenting and recruitment process.

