Procedure for Assessing Outcomes: Facility-level and resident-level outcomes will be obtained by trained research assistants (RAs) who are blind to facility condition (treatment versus control). To maintain blinding, these RAs will not be provided with information about randomization or details of the different interventions and we will keep all meetings of evaluation and intervention teams separate. Inter-rater reliability will be done on 10% of our outcome measures. Blinded RAs will obtain all resident descriptive and outcome data and descriptive facility data at baseline, 4 and 12 months from the following sources: designated administrative staff for facility relevant date (e.g., staffing); resident medical chart; and observations by the RAs and input

from the facility staff working with the resident at the time of evaluation (approximately 10 minutes of staff time). The Research Nurse Facilitator will obtain setting RE-AIM outcomes at baseline, 12 and 24 months in intervention sites only as delineated in Appendix E.

Measures are in Appendix F. Overview of each measure, measurement level, source of data, and timing of data collection are in Appendix E

Facility Descriptive Data

The following data will be obtained at baseline to describe facilities and consider confounders: state; size; profit or non-profit ownership status; urban or rural; Nursing Home Compare reported descriptives (11 outcomes such as percentage of residents with pain); staffing ratio and mix [at baseline, 4, 12 months: number of nursing assistants; nurses (registered; licensed practical nurses), and activity staff /number of residents].

Resident Descriptives

Resident descriptive information: age, race, gender, education, and marital status at baseline; psychotropics (antipsychotics, antidepressants, sedative/hypnotics, anxiolytics) obtained at baseline, 4 and 12 months.

Cognitive status will be measured at baseline using the Brief Interview of Mental Status (BIMS).¹²² The BIMS includes 3-item recall and orientation questions with scores ranging from 0 to 15. Prior use has provided evidence of reliability and validity.¹³²⁻¹³⁴

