Month 1-4 Initial Planning/Set Up	IRB/Staff training; facility recruitment; Cohort 1 Coordination with facilities; EIT-4-BPSD planning for training and identification of Internal Champions; listserv of Internal Champions and Stakeholders for weekly emails. EO planning for in-service.
Month 5-17 Cohort 1 Intervention	EIT-4-BPSD Intervention: 4-5 from Maryland; 4-5 from Pennsylvania; Implementation of Steps of EIT-4-BPSD; Recruitment of 12-13 residents per facility, complete assessments of residents and facilities including cost data.
	EO Intervention: 4-5 from Maryland; 4-5 from Pennsylvania; Coordinate and provide the educational intervention; Recruitment of 12-13 residents per facility and complete assessments of resident and facilities.
Month 18-20 Cohort 2 Set Up	Cohort 2-Coordination with facilities; planning for face-to-face training; and identification of Internal Champion.
Month 21-33 Intervention	EIT-4-BPSD Intervention: Same process as for Cohort 1; 18 and 24-month maintenance data collection for Cohort 1 (months 23 and 29)
	EO Intervention: Same process as for Cohort 1
Month 34-36 Cohort 3 Set Up	Cohort 3-Coordination with the Facilities; planning for face-to-face training and identification of Internal Champion.
Month 37-49 Intervention	EIT-4-BPSD Intervention: Same process as for Cohorts 1 and 2; 18 and 24 month maintenance data collection for Cohort 2 (months 39 and 45)
	EO Intervention: Same process as for Cohorts 1 and 2
Month 50-60	18 month maintenance data collection for Cohort 3 (month 55); Completion of data entry, analysis and manuscript development;

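### Table 3 gives cohort 3 no 24-month maintenance visit, so 8–9 of the 25 EIT-4-BPSD facilities lack a value that the text presents as collected in that arm

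*Combined protocol and SAP*

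**What the plan says.** Four parts of the protocol name 24 months for the intervention arm, and none restricts it to certain cohorts.

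- **Innovation, item 1:** "we examine maintenance in EIT-4-BPSD facilities at 24 months post implementation (which is 12 month post intervention activities"). Item 3 describes "maintenance at 12 months post completion of the intervention (24 months post implementation").
- **Methods, Design:** "We will also examine Maintenance in EIT-4-BPSD facilities at 24 months post implementation".
- **Procedure for Assessing Outcomes:** "The Research Nurse Facilitator will obtain setting RE-AIM outcomes at baseline, 12 and 24 months in intervention sites only as delineated in Appendix E". The same section says that measures, sources and "timing of data collection are in Appendix E".
- **Data Analysis, Maintenance:** the 24-month values enter two analyses, a linear mixed model (LMM) of change from baseline to 24 months and a comparison of 12 with 24 months.

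Table 3 gives the calendar. Cohort 1 has 18- and 24-month maintenance visits in study months 23 and 29, and cohort 2 has them in months 39 and 45. For cohort 3, the months 50–60 row lists "18 month maintenance data collection for Cohort 3 (month 55"), followed by data entry, analysis and manuscripts. It lists no 24-month visit.

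On cohorts, the Setting section says "the facility will be randomized to one of three cohort groups and then randomized to EIT-4-BPSD or EO", and then "We will implement EIT-4-BPSD in 8-10 facilities and the EO intervention in 8-10 facilities during each cohort period".

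**The concern.** A reader of the Design and Maintenance sections would take it that every intervention facility is observed a year after intervention activities end. Followed as printed, Table 3 cannot deliver that for the last cohort.

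Maintenance is one of the five RE-AIM criteria in the Aim 1 research question. The Innovation section presents the 24-month follow-up as a strength because staff tend to fall back into old habits. If about a third of the arm has no 24-month observation, the precision and the calendar coverage of that result are less than the text implies.

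There is a second, smaller point. Table 3 schedules an 18-month visit for all three cohorts, but neither the outcome procedures nor the Maintenance analysis mentions it.

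**Working it through.** **1. Visit months.** Table 3 starts the cohorts in months 5, 21 and 37. Study month of visit = start month + 18 or + 24.

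| Cohort | +18 | Table 3 | +24 | Table 3 |
|---|---|---|---|---|
| 1 | 5 + 18 = 23 | 23 | 5 + 24 = 29 | 29 |
| 2 | 21 + 18 = 39 | 39 | 21 + 24 = 45 | 45 |
| 3 | 37 + 18 = 55 | 55 | 37 + 24 = 61 | none |

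All five printed months reproduce, so no printed figure is miscalculated. Counting from the last intervention month gives the same answer for cohort 3 (49 + 12 = 61). Counting elapsed time from the start of month 37, 24 months end at the close of month 60. No visit is listed on either count.

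**2. Facilities affected.** The Adoption paragraph gives 25 EIT-4-BPSD facilities, and the Setting section gives 8–10 per cohort. The only way to make 25 from three numbers between 8 and 10 is 8 + 8 + 9, in some order. Cohort 3 therefore has 8 or 9 facilities (8/25 = 32%, 9/25 = 36%). The other two cohorts have 17 or 16 (68% or 64%).

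**3. Precision.** Let n (16 or 17) be the number of facilities with a 24-month value. The other 25 − n have all earlier visits. R is the standard error of a contrast under this schedule divided by its standard error with all 25 observed at 24 months. The estimates are generalised least squares with known covariance, which is what a maximum-likelihood LMM approximates. The plan gives no within-facility correlation, so the range 0 to 1 is shown.

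*Equal correlation between visits (facility random intercept), k earlier visits:*

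- Correlation 0: R² = (1 + 25/n)/2. For n = 17, √1.235 = 1.11. For n = 16, √1.281 = 1.13.
- Correlation approaching 1: R² = [(1 + 1/k)(25/n) + (1 − 1/k)]/2.
  - k = 1 (12 months only): R² = 25/n, so R = 1.21 (n = 17) or 1.25 (n = 16).
  - k = 2 (baseline, 12): √1.353 = 1.16 or √1.422 = 1.19.
  - k = 3 (baseline, 12, 18): √1.314 = 1.15 or √1.375 = 1.17.

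By symmetry, the baseline-to-24-month contrast has the same R for k = 2 and k = 3.

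*Correlation that decays with time (AR(1)), baseline included:*

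- 12-to-24 change without 18 months: R² = [(1 + s)(25/n) + (1 − s)]/2, where s is the 12-month correlation. R runs from 1.11 to 1.21 (n = 17) and from 1.13 to 1.25 (n = 16).
- 12-to-24 change with 18 months: R² = (1 + 25/n)/2 at any correlation, so R = 1.11 or 1.13.
- Baseline-to-24 without 18 months: the same, R = 1.11 or 1.13.
- Baseline-to-24 with 18 months: R² = (25/n + 1 + 2s)/[2(1 + s)]. R runs from 1.11 down to 1.06 (n = 17) and from 1.13 down to 1.07 (n = 16).

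**Increase in standard error over n = 16–17 and all correlations:**

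| Structure | Visits used (months) | 12-to-24 change | Baseline-to-24 |
|---|---|---|---|
| Equal correlation | 12, 24 | 11–25% | – |
| Equal correlation | 0, 12, 24 | 11–19% | 11–19% |
| Equal correlation | 0, 12, 18, 24 | 11–17% | 11–17% |
| AR(1) | 0, 12, 24 | 11–25% | 11–13% |
| AR(1) | 0, 12, 18, 24 | 11–13% | 6–13% |

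**The case against.** The strongest objections concern certainty and weight.

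- **Appendix E.** It holds the data-collection timing, was not available, and might restrict the 24-month visit. It could also give the 18-month visit a role, so that secondary point is conditional. But it cannot make Table 3 agree with the Innovation, Design and Maintenance text as printed.
- **Lost text.** The last row of Table 3 ends in a semicolon, so something may be missing after it. This is unlikely to be a cohort 3 visit: that entry is complete, with one visit and one month, and the table's own rule puts the 24-month visit outside the timeline.
- **Implied, not stated.** No sentence says that all 25 facilities are seen at 24 months. This is fair. The defect is an unreconciled text and schedule, not an arithmetic error.
- **Small consequence.** Facilities are randomised to cohorts, so the gap is administrative and gives no evident reason for selection bias. Maximum likelihood still uses cohort 3's earlier values. No power or precision target is set for Maintenance, so none is breached. All of this stands and limits the weight of the point.
- **The 4-month values.** The Adoption paragraph uses 4-month values of the same facility measures. If these enter the model, k = 3 without the 18-month visit, and the equal-correlation range is already 11–17%. Adding 18 months (k = 4) then gives only 11–16%. Under AR(1) the 4-month value changes nothing, and the gain from 18 months remains. Using the 18-month visit is therefore an improvement; either fix to the 24-month text resolves the contradiction without it.

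**Conclusion.** The concern holds. As scheduled, 8–9 of 25 EIT-4-BPSD facilities (32–36%) have no 24-month value, and at most 16–17 are observed then, before attrition. Cohort 3 would inform the 24-month estimate only through the model. Depending on contrast, visits used and correlation structure, the standard error is 6–25% larger than with all 25 observed; without the 18-month visit it is 11–25% larger.

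The facility count rests only on figures in the protocol. The precision range rests on an unstated correlation, taken from 0 to 1, and on the two covariance structures shown.

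The importance is minor to moderate and limited to Maintenance. What is lost is mainly precision and coverage of the last calendar period. It should be corrected because the text would otherwise overstate what is observed.

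**What to change.** Reconcile Table 3 with Innovation items 1 and 3, Design, Procedure for Assessing Outcomes, Maintenance and Appendix E, in one of two ways.

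- **(a) Schedule the visit.** List a 24-month visit for cohort 3, at the close of month 60 by elapsed time or in month 61 by Table 3's count, if the study period allows. The cost is 8–9 facility visits at or just after the end of a period now given to data entry, analysis and manuscripts.
- **(b) Restrict the statement.** Say in those four parts of the protocol that 24-month values are observed in cohorts 1 and 2 only, 16–17 facilities before attrition. The cost is wording. The downside is a smaller stated 24-month number, and a result for all cohorts that reaches 6 rather than 12 months beyond intervention activities.

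In either case, add 18 months to the time points under Procedure for Assessing Outcomes, after checking Appendix E, and replace the Maintenance model sentence with:

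*An LMM fitted by maximum likelihood to all EIT-4-BPSD facilities will include facility-level measures at baseline, 12, 18 and 24 months, with facility as a random effect; the 18-month (all cohorts) and 24-month results will each be reported with the number of facilities observed.*

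This needs no new visits, because Table 3 already schedules 18 months for every cohort. It leaves the 4-month adoption analysis as it is. If Appendix E confirms that 4-month facility values are collected, they can be added to the model's list.
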